### **11.3.4 Hyperglycemic/Ketotic Events**

Hyperglycemia is only reportable as an adverse event when any one of the following criteria is met:

- The event involved DKA, as defined by the Diabetes Control and Complications Trial (DCCT) and described below
- Evaluation or treatment was obtained at a health care provider facility for an acute event involving hyperglycemia or ketosis, or the participant contacted the site and received guidance on how to manage the hyperglycemia/ketosis
- Prolonged hyperglycemia: defined as meter BG  $\geq 300$  mg/dL and ketones  $>1.0$  mmol/L
- Hyperglycemia resulting in an SAE that may not otherwise meet the above criteria

Hyperglycemic events are classified as DKA if all of the following are present:

- Symptoms such as polyuria, polydipsia, nausea, or vomiting;
- Serum ketones  $>1.5$  mmol/L or large/moderate urine ketones;
- Either arterial blood pH  $<7.30$  or venous pH  $<7.24$  or serum bicarbonate  $<15$ ; and
- Treatment provided in a health care facility

When a hyperglycemia/ketotic event meets the above reporting requirements, Adverse Event Form should be completed.

Events meeting DKA criteria should be considered a serious adverse event and follow the SAE reporting requirements. Hyperglycemia events not meeting criteria for DKA generally will not be considered as serious adverse events unless one of the SAE criteria above is met.

#### **11.3.5 Relationship of Adverse Event to Investigational Device**

The investigator will be responsible for making a determination on the causal relationship of the AE. Specifically, the investigator will report whether the AE was related to study procedures and/or related to the investigational device.

To ensure consistency of adverse event causality assessments, investigators should apply the following general guideline when determining whether an adverse event is related:

The causal relationship to the study procedures and the investigational device for each adverse event will be rated as follows:

- Unrelated: The event is not related to the procedures or the investigational device.
- Possibly Related: The temporal sequence is such that the relationship is not unlikely or there is no contradicting evidence that can reasonably explain the subject's condition. There is a possibility of any relation between the event and the procedures or the investigational device.
- Related: The temporal sequence is relevant or the event abates upon completion of the procedure/ investigational device, or the event cannot be reasonably explained by the subject's condition or comorbidities. The event is related or most likely associated with the procedures or the investigational device.

#### **11.3.6 Severity (Intensity) of Adverse Events**

The severity (intensity) of an adverse event will be rated on a three-point scale: (1) mild, (2) moderate, or (3) severe. A severity assessment is a clinical determination of the intensity of an event. Thus, a severe adverse event is not necessarily serious. For example, itching for several days may be rated as severe, but may not be clinically serious.

- **MILD**: Usually transient, requires no special treatment, and does not interfere with the participant's daily activities.

- MODERATE: Usually causes a low level of inconvenience, discomfort or concern to the participant and may interfere with daily activities but is usually ameliorated by simple therapeutic measures and participant is able to continue in study.
- SEVERE: Interrupts a participant's usual daily activities, causes severe discomfort, may cause discontinuation of study device, and generally requires systemic drug therapy or other treatment.

#### 11.3.7 Outcome of Adverse Events

The outcome of each reportable adverse event will be classified by the investigator as follows:

- RECOVERED/RESOLVED - The participant recovered from the AE/SAE without sequelae. Record the AE/SAE stop date.
- RECOVERED/RESOLVED WITH SEQUELAE - The event persisted and had stabilized without further anticipated change in the event status. Record the AE/SAE stop date.
- FATAL - A fatal outcome is defined as the SAE that resulted in death. Only the event that was the cause of death should be reported as fatal. AEs/SAEs that were ongoing at the time of death; however, were not the cause of death, will be recorded as "resolved" at the time of death.
- NOT RECOVERED/NOT RESOLVED (ONGOING) - An ongoing AE/SAE is defined as the event was ongoing with an undetermined outcome.
  - An ongoing outcome will require follow-up by the site in order to determine the final outcome of the AE/SAE or until participant completes the study.
  - The outcome of an ongoing event at the time of death that was not the cause of death, will be updated and recorded as "resolved" with the date of death recorded as the stop date.
- UNKNOWN - An unknown outcome is defined as an inability to access the participant or the participant's records to determine the outcome (for example, a participant that was lost to follow-up).

If any UADEs are ongoing when a participant completes the study (or withdraws), the subject will continue to be followed until the event resolves or has no prospect of improvement or change, even after the participant has completed all applicable study visits/contacts, unless that subject has withdrawn their consent. For all other reportable adverse events, data collection will end at the time the participant completes the study. Note: Participants should continue to receive appropriate medical care for an adverse event after their participation in the study ends.

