## 9.7 Visit 10 (End of Study)

**Visit 10** will be conducted in person at the clinical study site. All scheduled assessments will be performed according to Table 2: Schedule of Assessments. If the subject has not experienced any serious adverse events, and continue to meet eligibility requirements, the subject will be deemed eligible to participate in the pivotal study. This visit will conclude their participation in the prepivotal study. This visit will include:

- Review of concomitant medications
- Height
- Weight

- Assessment of vital signs
- Assessment of AEs since last visit
- Completion of questionnaires (see Table 3: Questionnaires for specific requirements by age group) :
  - WHO-5
  - EQ-5D
  - T1DDS
  - DTSQc
  - Hypoglycemia Confidence Scale
  - HABS
  - PSQI
  - IDSS (T1)
  - SUS
  - PAID-(Teen, Child)
  - INSPIRE-(Adult, Youth, Parent)
    - Used to measure a caregiver's experience of the support they receive
  - Clarke
  - Human Factors (HF) Questionnaire
    - Measures trust in the Horizon™ System
- Discontinuation of remote monitoring
- Return study devices (Omnipod Horizon™ System, CGM, BG and ketone meters if not extending into pivotal study)
- Complaints/device deficiencies such as occlusion alarms and system hazard alarms since last visit
- Device uploads for BG and ketone meter
- Data review by clinician

For subjects not extending their participation into the pivotal study, they will return their study devices to the site and their participation in the study will end.

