## 11 SAFETY

### 11.1 Types of Known Risks and Benefits

There are known risks and benefits. Most of the risks are not unique to the study and are typical for patients using insulin pumps, CGM, and BG meters.

The known risks are as follows:

- Hypoglycemia and/or hyperglycemia as a result of change in diet, activity, diabetes management or insulin regimen during the study.
- Hypoglycemia, hyperglycemia, diabetic ketoacidosis, seizure, coma or death related to insulin administration, pump use or misuse, or Horizon™ System use or misuse.
- Use of the Pod (Omnipod® tubeless, insulin delivery pump) - Because the Pod uses only rapid-acting insulin, users are at increased risk for developing hyperglycemia if insulin delivery is interrupted. If it is untreated, prolonged hyperglycemia can quickly lead to diabetic ketoacidosis (DKA). DKA can cause symptoms such as breathing difficulties, shock, coma, or death. Further, occlusions can interrupt insulin delivery and lead to hyperglycemia or DKA. Other potential risks associated with using the Pod are:
  - Anaphylaxis (allergic shock)
  - Bruising at the Pod site
  - Bleeding at the Pod site
  - Erythema (redness at the Pod site)
  - Excoriation (raw skin at Pod site)
  - Pruritus (itching)
  - Induration (hardening of the skin at the Pod site)
  - Infection (can include heat, redness, swelling, pain, and drainage)
  - Inflammation (redness, swelling)
  - Skin reaction to adhesive at the Pod site
  - Papule (small, solid raised area on the skin similar to a pimple)
  - Pain or discomfort

- Ulceration (skin sores)
- Vesicles (blisters)
- Use of the CGM - risk of bruising, infection, pain and/or bleeding at the site of insertion, and skin site reaction to adhesive.
- On rare occasions, the CGM sensor may break and leave a small portion of the sensor under the skin that may cause redness, swelling, or pain at the insertion site, and may require surgical removal.
- Blood sampling with fingerstick - minor discomfort and risk of infection at site of fingerstick.

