## 11.3 Adverse Events

### 11.3.1 Definitions

**Adverse Event (AE):** is defined as any untoward medical occurrence, unintended disease or injury, or any untoward clinical signs (including an abnormal laboratory finding) in subjects, users or other persons, whether or not related to the investigational medical device.

NOTE 1: This includes events related to the investigational medical device or the comparator.

NOTE 2: This definition includes events related to the procedures involved (any procedure in the clinical investigation plan).

**Serious Adverse Event (SAE):** Any untoward medical occurrence that:

- Led to death
- Led to serious deterioration in the health of the subject, that either resulted in:
  - a life-threatening illness or injury, or
  - a permanent impairment of a body structure or a body function, or
  - in-patient or prolonged hospitalization, or
  - medical or surgical intervention to prevent life-threatening illness or injury or permanent impairment to a body structure or a body function.
- Led to fetal distress, fetal death, or a congenital abnormality or birth defect.

NOTE: Planned hospitalization for a pre-existing condition, or a procedure required by the clinical investigational plan, without serious deterioration in health, is not considered a serious adverse event.

**Unanticipated Adverse Device Effect (UADE):** Any serious adverse effect on health or safety or any life-threatening problem or death caused by, or associated with, a device, if that effect, problem, or death was not previously identified in nature, severity, or degree of incidence in the investigational plan or application (including a supplementary plan or application), or any other unanticipated serious problem associated with a device that relates to the rights, safety, or welfare of participants.

**Adverse Device Effect (ADE):** An adverse device effect is an adverse event related to the use of an investigational medical device.

NOTE 1: This definition includes any adverse event resulting from insufficient or inadequate instructions for use, deployment, implantation, installation, or operation, or any malfunction of the investigational medical device.

NOTE 2: This definition includes any event resulting from user error or from intentional misuse of the investigational medical device.

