### **11.3.2 Reportable Adverse Events**

Adverse events will be assessed on an ongoing basis throughout the study. Adverse event reporting will begin at the start time of the standard therapy phase (i.e., insertion of the CGM sensor) and continue through the hybrid closed-loop phase until the subject's participation has ended. All adverse events must be followed until resolution, or until the AE has stabilized, or until the study has been completed.

Pre-existing medical conditions or symptoms observed prior to the start time of the standard therapy phase will not be recorded as an AE and should be collected in the subject's medical history. In the event there is a change (i.e., worsening) in the pre-existing medical condition or symptoms after enrollment meeting the criteria of a reportable adverse event, then an AE must be reported.

For this protocol, a reportable adverse event includes any untoward medical occurrence that meets one of the following criteria:

1. An SAE
2. An ADE unless excluded from reporting in Hypoglycemic Events and Hyperglycemic/Ketotic Events sections below
3. An AE occurring in association with a study procedure
4. An AE not related to a study device issue which leads to temporary or permanent discontinuation of the study device
5. An AE that affects the participant's ability to complete any study procedures
6. An AE for which a visit is made to a hospital emergency department
7. Hypoglycemic Events as defined below
8. Hyperglycemic/Ketotic Events as defined below.

Skin reactions from sensor or pod placement are only reportable if severe and/or required treatment.

For the purpose of this protocol, mild symptoms of hypoglycemia and hyperglycemia (i.e., clinically non-significant) or blood glucose values out of the normal range (whether or not they resulted in delayed meals or correction boluses) will not be reported as AEs unless determined to meet the reportable criteria in the Hypoglycemic Events and Hyperglycemic/Ketotic Events sections below.

All reportable AEs—whether volunteered by the participant, discovered by study personnel during questioning, or detected through physical examination, laboratory test, or other means—will be reported on an AE eCRF.

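### Follow-up after study exit covers only UADEs, so the final outcome of an anticipated serious device-related event still ongoing at exit is not collected

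*Protocol*

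**What the plan says.** Protocol 11.3.7 has two rules for events open at the end of a subject's participation. The first covers UADEs: "If any UADEs are ongoing when a participant completes the study (or withdraws), the subject will continue to be followed until the event resolves". That follow-up also stops once no further change is expected, and it does not apply if consent is withdrawn. The second covers everything else: "For all other reportable adverse events, data collection will end at the time the participant completes the study". No exception is made for serious or device-related events. The outcome category for unresolved events in the same section has the same limit: "An ongoing outcome will require follow-up by the site in order to determine the final outcome of the AE/SAE or until participant completes the study".

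Section 11.3.2 words its general rule differently: "All adverse events must be followed until resolution, or until the AE has stabilized, or until the study has been completed".

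Participation ends at Visit 10 (9.7): "This visit will conclude their participation in the prepivotal study". Eligibility for the pivotal study is stated there under a condition: "If the subject has not experienced any serious adverse events, and continue to meet eligibility requirements".

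Under 11.3.1, a serious device effect is a UADE only if it "was not previously identified in nature, severity, or degree of incidence in the investigational plan" or application. The known risks in 11.1 include "Hypoglycemia, hyperglycemia, diabetic ketoacidosis, seizure, coma or death related to insulin administration, pump use or misuse", and the same item extends to use or misuse of the Horizon System.

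The SAP's safety section (5 to 5.5) has no rule on follow-up after exit.

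**The concern.** The exception for UADEs leaves out the serious harms that the plan itself expects. Severe hypoglycemia and DKA are the two secondary safety endpoints, and when device-related they are the obvious candidates for the primary safety endpoint. Because they are listed as known risks, they will normally be anticipated, and so fall under the rule that stops data collection at exit.

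At stake is the record of how harmed subjects fared: whether the event resolved, left sequelae or worsened. The DSMB reviews safety at the conclusion of this study and comments on continuing the pivotal study (11.8), so open outcomes would be missing where they are most useful. A second, smaller matter is that two sections give sites different dates on which to stop following an event.

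**Working it through.** The plan states no figure on this point. The check reads the rules in sequence for a device-related DKA or severe hypoglycemia that is ongoing at exit.

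1. **Is it serious?** Yes, by definition: 11.3.3 for severe hypoglycemia and 11.3.4 for DKA.
2. **Is it a UADE?** Normally not. The 11.3.1 definition excludes effects already identified, and 11.1 identifies these. An event of unexpected severity or incidence could still qualify; the Medical Monitor reviews serious related events for this (11.9).
3. **Which follow-up rule applies?** If it is not a UADE, it falls under the rule for all other reportable events in 11.3.7, which ends with completion.
4. **When is that?** Table 2 puts Visit 10 at day 14, with a window of +2 days, so exit falls on days 14 to 16. The time available is the exit day minus the onset day:
   - onset on day 12: 14 − 12 = 2 to 16 − 12 = 4 days
   - onset on day 14: 14 − 14 = 0 to 16 − 14 = 2 days
5. **What about withdrawal?** The stop sentence in 11.3.7 names completion only, but 11.3.2 runs adverse event reporting until participation has ended, and 9.9 ends participation at withdrawal. Under 11.7.1 a single DKA or severe hypoglycemia event can itself lead to withdrawal, so the event can cause the exit that ends its own follow-up.
6. **Does anything else take over?** The pivotal study is not a planned route, because 9.7 states eligibility only for subjects with no serious adverse event. Section 11.5 asks for the discharge summary of a hospitalized subject, and 11.9 provides adjudication. Neither requires follow-up to resolution. The closing note in 11.3.7 concerns medical care, not data.

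The effect on the primary safety endpoint depends on the state of the event at exit. That endpoint (6.1.1) is the proportion of subjects with a serious device-related event, so it counts occurrence.

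| Related event at exit | Counted in the endpoint? | What is not collected |
|---|---|---|
| Serious, UADE, ongoing | Yes | Nothing; it is followed |
| Serious, anticipated, ongoing | Yes, already | Final outcome, sequelae, later worsening |
| Non-serious, becomes serious after exit | Not if no one records the change | The change in seriousness |

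Only the third row can alter the count. For scale, one subject is 1/36 = 2.8% at the minimum evaluable number and 1/48 = 2.1% at the maximum enrollment. This is the step size of the endpoint, not an estimate of undercounting; that would need a rate of late worsening, which the documents do not give.

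**End points compared.** Section 11.3.2 stops when the study is completed, 11.3.7 when the participant completes it. If the first means the whole study, its date can lie well beyond day 14 to 16, since the Protocol Summary expects the study to take up to 6 months. The two sections then conflict.

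**The case against.** A reader might infer that the cut-off biases the primary safety proportion downward. The documents do not support that. DKA and severe hypoglycemia are serious by definition, so a case open at Visit 10 is already counted. SAP 3.1 summarizes the safety endpoints during hybrid closed-loop (HCL), and SAP 1 gives the SAP precedence, so worsening after that phase is arguably outside the endpoint rather than wrongly omitted from it. A share of events still open at exit, computed from an assumed duration, would not measure bias either: the time to resolve and the time to become serious are different quantities, and the documents give neither.

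Nor can it be said that late worsening of a non-serious event would never be recorded. Such a subject may well enter the pivotal study: inclusion criterion 8 requires willingness to do so, and the subject number is kept (7.1). The pivotal protocol is not among the documents, so what it would capture is unknown.

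Other provisions soften the gap: the discharge summary, adjudication with no stated cut-off at Visit 10, DSMB notification of every severe hypoglycemia and DKA case (11.6), and the wider reading of 11.3.2. Safety is also descriptive, with no hypothesis tests (SAP 5.4) and no success criterion (SAP 2.5).

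These arguments dispose of the bias claim and limit the weight of the point. They do not close the gap: none requires the final outcome of an anticipated serious device-related event to be obtained after exit.

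**Conclusion.** The point holds as a gap in outcome data. An anticipated serious device-related event that is ongoing at Visit 10 or withdrawal is counted, but its final outcome and sequelae are not collected, and the plan does not route that subject into the pivotal study. Late-onset events are most exposed, with 0 to 4 days available for onset from day 12 to day 14 in a subject who completes.

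Undercounting in the primary safety endpoint is possible only through a related non-serious event that becomes serious after exit; its size cannot be estimated from the documents. Sections 11.3.2 and 11.3.7 need to be reconciled in any case.

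The conclusion assumes that such events are classed as anticipated, as 11.1 and 11.3.1 imply. It concerns study data only, since 11.3.7 says medical care should continue. With few subjects and descriptive safety reporting, this is a cheap improvement rather than a flaw that threatens the study's conclusions.

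**What to change.** - **Protocol 11.3.7:** extend the UADE follow-up sentence to any serious adverse event rated related or possibly related to the device or study procedures that is ongoing at completion or withdrawal. Keep the existing stop rule (resolved, or no prospect of change, unless consent is withdrawn), and apply it whether or not the subject enters the pivotal study. Make the sentence on all other events, and the text for ongoing outcomes, consistent with this.
- **Protocol 11.3.2:** align the general rule, stating whether follow-up ends with the participant's completion or with the whole study.
- **SAP 3.1 and 5.4:** add matching wording that later outcomes, and later changes in seriousness, of events with onset during HCL are reported descriptively. The endpoint should not be changed in the protocol alone, because the SAP prevails where the two differ.

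The cost is a few sentences, a few telephone contacts by existing site staff, and a short delay in closing those records. Treatment and the visit schedule are unaffected.

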#### 11.4 Reportable Device Issues

Device complaints and malfunctions will be reported except in the following circumstances. These occurrences are expected and will not be reported on a Device Deficiency Form:

- CGM sensor or Pod lasting fewer days than expected per manufacturer
- CGM tape or Pod adherence issues

- Battery lifespan deficiency due to inadequate charging or extensive wireless communication
- Intermittent device component disconnections/communication failures not requiring system replacement or workaround/resolution not specified in user guide/manual.
- Device issues clearly addressed in the user guide manual that do not require additional troubleshooting

## 11.5 Timing of Event Reporting

SAEs possibly related or related to a study device or study procedures and UADEs must be reported to the Sponsor/CRO within 2 business days of the site becoming aware of the event. This can occur via phone or email, or by completion of the AE eCRF. If the form is not initially completed, it should be completed as soon as possible after there is sufficient information to evaluate the event. All other reportable AEs should be submitted by completion of the AE eCRF within 5 business days of the site becoming aware of the event.

Each principal investigator is responsible for reporting adverse events required by this protocol and abiding by any other reporting requirements specific to his/her Institutional Review Board or Ethics Committee.

Upon receipt of a UADE report, the Sponsor will investigate the UADE and if indicated, report the results of the investigation to all participating investigators, overseeing IRBs, and the FDA within 10 business days of the Sponsor becoming aware of the UADE per 21CFR 812.46(b). Copies of the associated reports and correspondence with the investigators, regulatory authorities, and Sponsor must be retained with study records.

The Medical Monitor must notify the DSMB of any UADEs and determine if the UADE presents an unreasonable risk to participants. If so, the Sponsor must ensure that all investigations, or parts of investigations presenting that risk, are terminated as soon as possible but no later than 5 working days after the Medical Monitor makes this determination and no later than 15 working days after first receipt notice of the UADE.

Device deficiencies will be handled by the Sponsor or designee as described below. In the case of a Dexcom CGM transmitter or sensor device malfunction, information should be forwarded to Dexcom by the site personnel, to be handled by Dexcom's complaint management system.

If the subject is hospitalized because of or during the course of an SAE, then a copy of the hospital discharge summary must be requested for inclusion with the SAE documentation. In case of death, the investigator must make every effort to obtain a copy of the death certificate to submit to the Sponsor. When submitting copies of documentation, all subject identifying information must be redacted and only the unique subject number will be used to label the forms for identification purposes.

For any event where there is suspicion that the study device is involved, the investigator will return the device for evaluation when possible.

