### **11.3.3 Hypoglycemic Events**

Hypoglycemia is only reportable as an adverse event when one of the following criteria is met:

- Severe Hypoglycemia: The event required assistance of another person due to altered consciousness, and required another person to actively administer carbohydrate, glucagon, or other resuscitative actions. This means that the participant was impaired cognitively to the point that he/she was unable to treat himself/herself, was unable to verbalize his/her needs, was incoherent, disoriented, and/or combative, or experienced seizure or loss of consciousness. These episodes may be associated with sufficient neuroglycopenia to induce seizure or loss of consciousness. If plasma glucose measurements are not available during such an event, neurological recovery attributable to the restoration of plasma glucose to normal is considered sufficient evidence that the event was induced by a low plasma glucose concentration.
- Hypoglycemia resulting in an SAE that may not otherwise meet the definition of Severe Hypoglycemia defined above.

When a hypoglycemic event meets the above reporting requirements, an Adverse Event Form should be completed. A severe hypoglycemia event should be considered a serious adverse event and follow the SAE reporting requirements.

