## 11.6 Safety Oversight

The study Medical Monitor will review all adverse events that are reported during the study. SAEs will typically be reviewed within 24-hours of reporting. Other AEs will typically be reviewed approximately weekly.

A Data and Safety Monitoring Board (DSMB) will be informed of all cases of severe hypoglycemia and diabetic ketoacidosis irrespective of device relationship and all UADEs during the study and will review compiled safety data at periodic intervals. The DSMB also will be informed of any SAEs and ADEs not meeting criteria for a UADE if the Medical Monitor requests the DSMB review. The DSMB can request modifications to the study protocol or suspension or outright stoppage of the study if deemed necessary based on the totality of safety data available. Details regarding DSMB review will be documented in a separate DSMB Charter.

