## 11.7 Stopping Criteria

### 11.7.1 Participant Discontinuation of Study Participation

In the case of a UADE, use of the study device will be suspended while the problem is diagnosed. After assessment of the problem and any correction, use of the study device will not be restarted until approval is received from the IRB, DSMB, and FDA.

Use of the study device by a participant will be discontinued if any of the following occur:

- The investigator believes it is unsafe for the participant to continue on the intervention. This could be due to the development of a new medical condition or worsening of an existing condition; or participant behavior contrary to the indications for use of the device that imposes on the participant's safety.
- The participant requests that the treatment be stopped
- Participant pregnancy
- Two distinct episodes of DKA as defined above
- Two distinct severe hypoglycemia events as defined above
- One episode of DKA and one severe hypoglycemia event as defined above

An additional requirement for continued study device use following a single DKA or severe hypoglycemia event will be that (1) the site investigator believes that the event is explainable, unlikely to recur, and that it is safe for the participant to continue to use the system and (2) the Medical Monitor concurs. If the Medical Monitor determines that the occurrence of the event indicates that it is not safe for the participant to continue to use the system, use will be discontinued, and the subject will be withdrawn from the study.

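### The reporting deadline for DKA and severe hypoglycemia depends on the site's relatedness rating, although Medical Monitor concurrence, which has no stated timing, is required whatever the cause

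*Protocol*

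**What the plan says.** Protocol Section 11.3.3 says: "A severe hypoglycemia event should be considered a serious adverse event and follow the SAE reporting requirements". Section 11.3.4 says the same of DKA: "Events meeting DKA criteria should be considered a serious adverse event and follow the SAE reporting requirements". Neither section gives a deadline. Section 14.8 likewise refers investigators to the timeline elsewhere in the protocol.

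The deadlines are in Section 11.5, which has two. The shorter one reads: "SAEs possibly related or related to a study device or study procedures and UADEs must be reported to the Sponsor/CRO within 2 business days"; it can be met by phone, email or eCRF. The longer one is residual: "All other reportable AEs should be submitted by completion of the AE eCRF within 5 business days of the site becoming aware". Relatedness at this stage is the site's rating. Under Section 11.3.5, "the investigator will report whether the AE was related to study procedures and/or related to the investigational device".

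Three provisions apply to these events whatever their cause:

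- **Section 11.6:** the DSMB is to be "informed of all cases of severe hypoglycemia and diabetic ketoacidosis irrespective of device relationship".
- **Section 11.7.1:** the relevant paragraph begins "An additional requirement for continued study device use following a single DKA or severe hypoglycemia event will be that" and sets two conditions. The investigator must judge the event explainable, unlikely to recur and safe to continue after, and the Medical Monitor must concur.
- **Section 11.9 (and SAP Section 5.1):** the Medical Monitor adjudicates all SAEs and all DKA and severe hypoglycemia events, including their relatedness.

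On speed of review, Section 11.6 says "SAEs will typically be reviewed within 24-hours of reporting", so that interval starts at the report and not at the event.

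**The concern.** Sections 11.3.3 and 11.3.4 refer to SAE reporting requirements as if there were one set. Section 11.5 has no deadline for SAEs as a class. It splits them by relatedness, and an SAE rated unrelated to both device and procedures falls under the residual 5-business-day rule. The UADE route would not ordinarily rescue it, because hypoglycemia, seizure, coma and DKA are listed as known risks in Section 11.1.

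How soon the Medical Monitor hears of the event is therefore set by the causality rating that the Medical Monitor is there to adjudicate. Section 11.7.1 adds no timing of its own. It gives no time by which concurrence must be sought or given, and it does not state the status of device use while concurrence is pending. The only explicit suspension in that section is for a UADE.

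What is at stake is an individual safeguard in a 14-day exposure that includes children from age 6. A site can meet Section 11.5 in full while the second opinion required by Section 11.7.1 arrives after closed-loop use has ended, or after a second event, which would itself require discontinuation. The DSMB's count of these events at its first review (after 16 subjects have at least 10 days of use, Section 11.8) could lag in the same way.

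**Working it through.** The plan gives no figure of its own to reproduce, so the check is a calendar count.

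**Inputs**

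- Deadlines of 2 and 5 business days (Section 11.5).
- Review about 1 day after the report (Section 11.6, stated as typical).
- Closed-loop phase of 14 days (Section 9); Visit 10 on day 14, up to 2 days later (Table 2).

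**Assumptions**

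- The site learns of the event on the day it happens; that day is day 0 of the lag.
- Weekends are skipped and there is no public holiday.
- The site uses its full allowance.

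**Formula:** day of review = day of awareness + calendar lag + 1. Review is late if this exceeds 14.

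| Awareness weekday | 5 business days: report lag / with review | First late day | 2 business days: report lag / with review | First late day |
|---|---|---|---|---|
| Mon, Tue, Wed | 7 / 8 | 7 | 2 / 3 | 12 |
| Thu, Fri | 7 / 8 | 7 | 4 / 5 | 10 |
| Sat | 6 / 7 | 8 | 3 / 4 | 11 |
| Sun | 5 / 6 | 9 | 2 / 3 | 12 |

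**Example.** The site learns of the event on a Friday that is day 7. A report the next Friday (day 14) is on time. Review a day later is day 15.

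**Count over 7 weekdays × 14 days = 98 combinations**

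- 5 business days: Monday to Friday, days 7–14, 5 × 8 = 40; Saturday, days 8–14, 7; Sunday, days 9–14, 6. Total 53 of 98 (54%).
- 2 business days: Monday to Wednesday and Sunday, days 12–14, 4 × 3 = 12; Thursday and Friday, days 10–14, 2 × 5 = 10; Saturday, days 11–14, 4. Total 26 of 98 (27%).

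The combinations are weighted equally. They describe what the deadlines allow and are not the probability of a late review.

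**Sensitivity**

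- Against the latest Visit 10 (day 16), the 5-business-day thresholds move to day 9 (longest lag) and day 11 (shortest). The count is 5 × 6 + 5 + 4 = 39 of 98 (40%).
- One public holiday can stretch the 5-business-day report lag to as much as 10 calendar days.
- For awareness on days 1–6, the base case always gives review by day 14.

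**The case against.** The strongest reply is that Section 11.7.1 makes concurrence a condition of continued use and does not tie it to the AE form. Section 11.5 sets the latest time for a report; it does not say that the Medical Monitor must be approached by that route. A site that kept a subject on the device without concurrence would breach Section 11.7.1 even if its eCRF was on time. This stands. A reader might infer that the protocol lets the subject continue for a week without concurrence, and the text does not support that. What remains is that the timing and the interim status are not stated.

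A reader might also infer that no other deadline for telling the Medical Monitor exists anywhere. That cannot be checked. Section 11.9 places the Medical Monitor's duties in the Safety Management Plan, and Sections 11.6 and 11.8 leave DSMB detail to the Charter; neither is among the documents. The supportable statement is that the protocol gives no other deadline.

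The affected set is also likely to be small. Section 11.3.5 defines Possibly Related broadly, Section 11.3.1 counts user error and misuse as device effects, and the investigational Pod delivers the insulin in this phase. As a rough guide, the largest adult percentages in Table 6 sum to 7% + 3% = 10%, with no period stated. If annual, 48 × 0.10 × 14/365 is about 0.2 subjects; if they cover three months (91 days), 48 × 0.10 × 14/91 is about 0.7. Both are before restricting to unrelated ratings. Table 6 defines severe hypoglycemia more narrowly than Section 11.3.3, so these figures are only indicative.

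Other safeguards do not wait for the Medical Monitor. Remote alerts reach site staff (Section 3.1), device use stops if the investigator believes it unsafe (Section 11.7.1), and an SAE bars entry to the pivotal study (Section 9.7). They lower the risk, but they do not replace the required second opinion.

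On the DSMB, the two deadlines differ by only 3 to 5 calendar days, and no effect on its first review is shown. That part is minor.

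**Conclusion.** The point holds as a mismatch within the protocol. Sections 11.6, 11.7.1 and 11.9 act on severe hypoglycemia and DKA regardless of cause, while Section 11.5 sets the reporting deadline by the site's relatedness rating. For events rated unrelated to both device and procedures, an on-time report can reach Medical Monitor review 6 to 8 calendar days after awareness. Review can then fall after day 14 for events known from day 7 at the longest lag, or from day 9 at the shortest.

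This rests on sites using the full allowance and on review within the typical 24 hours. The 5 business days are a maximum, and sites may report sooner. The documents give no expected share of unrelated ratings.

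The reporting deadline is only part of the cause, because the 2-business-day deadline also allows late review for awareness from days 10 to 12. The silence of Section 11.7.1 on timing and interim status belongs equally to the finding. Given the few events likely to be affected and the other safeguards, this should be fixed but does not rank as a must-fix.

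**What to change.** In Section 11.5, place every severe hypoglycemia and DKA event, or simply every SAE, under the existing 2-business-day deadline by phone, email or eCRF, whatever the relatedness rating. Point Sections 11.3.3 and 11.3.4 to that deadline explicitly.

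The sponsor must also reconcile Section 11.5 with Section 11.7.1 on when concurrence is to be obtained and on the status of device use until then. That is a clinical rule for the sponsor to set, and none is proposed here.

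The cost is about one sentence in Section 11.5, two cross-references, the reconciling text, and matching eCRF and Safety Management Plan wording. A few events would be reported sooner, by routes the protocol already allows, with no added study procedures.
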